6.4 Study Assessments

(ICH E3; 9.5.1. ICH E9; 2.2.2)

Visit	Baseline	Every Visit	Visit Month 12
History and examination	x	x	x
QOL questionnaire	x	x (\pm 14)	x (\pm 14)
MISS	x	x (\pm 14)	x (\pm 14)
Actionable AEs	x	x	x
SAEs	x	x	x
SUSARs	x	x	x
Concomitant medication	x	x	x
Methotrexate use and dose	x	x	x
Ondansetron use and dose	x	x	x

Analysis Time Windows

Visit (target day)	Lower bound (days)	Upper bound (days)
Baseline (0)	N/A	N/A
Every visit to clinic (time window not applicable)	N/A	N/A
Month 4-8 (180)	120	240
Month 12 (364)	308	420

7 Sample Size

(ICH E3; 9.7.2. ICH E9; 3.5)

Our primary outcome statistic is the ratio of two proportions (relative risk, RR): the proportion of randomized children remaining on methotrexate with no intolerance in the intervention group divided by the same in the control group. Our sample size calculation is based on expressing the RR in the log scale and using established formulas for standard errors [15, 16]. With $p<0.05$, power of 90% and expected methotrexate continuation with no intolerance of 50% in the control group and 75% in the intervention group the result is 79 evaluable subjects per group. We will aim to recruit 176 subjects total to allow for up to a 10% dropout rate.

8 General Analysis Considerations

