8.5.6 Adjustment of Confidence Intervals and p-values

We use the O'Brien-Fleming adjustment to type 1 error rate for the interim analysis. This adjustment is based on the “alpha-spending” principle that guarantees that no conclusions from the trial have more than a 5% chance of a positive result if the intervention is no more effective than control. The adjustment uses a substantially reduced alpha level for the interim analysis, making it more difficult to terminate the trial prematurely due to chance outcomes. The final analysis of the primary outcome uses the remaining alpha not used (0.05 minus the amount used in the interim, 0.0045), and combines the data from both stages of the trial into one final test statistic.

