8.5.7 Interim Analysis for Sample Size Adjustment

Upon completion of the interim analysis, a new sample size estimate is calculated using simulation techniques. Simulation answers the following question: given our current data, and assuming that our initial expectations for success probability in the two arms remain true (75% in intervention, 50% in control), how many more patients would need to be enrolled in order to maintain a 90% chance that the final analysis produces a 95% confidence interval for the relative risk that lies entirely above 1.2?

We use simulation techniques because the binary success/failure outcome is easy to simulate accurately from any expected probability specifications and for any size of patient sample. The simulation involves creating hypothetical future results using the expected success probabilities for a new set of n patients in each treatment group, adding the current results to these simulated future results, conducting the final analysis on the complete set of results, and observing whether the confidence interval lies entirely above 1.2. We perform this simulation and analysis process 10,000 times, and the proportion of these replicates in which the interval lies above 1.2 is an accurate estimate of the power for the study using n new patients per group. By repeating the process for a variety of values of n , we can identify the smallest sample size that achieves 90% power.

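### The sample-size re-estimation returns a number to enrol without dropout or the final alpha, so that number gives about 86% to 88.5% power, not 90%, if 10% drop out

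*SAP*

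**What the plan says.** Section 8.5.7 poses its question in terms of enrolment: "how many more patients would need to be enrolled in order to maintain a 90% chance". Success is defined in the same place by the requirement that "the final analysis produces a 95% confidence interval for the relative risk that lies entirely above 1.2". The rates for new children are set by "assuming that our initial expectations for success probability in the two arms remain true (75% in intervention, 50% in control"). The reason given for simulating is that "the binary success/failure outcome is easy to simulate accurately from any expected probability specifications". Each replicate is described as "creating hypothetical future results using the expected success probabilities for a new set of n patients in each treatment group". Interim results are then pooled with these, the planned final analysis is run, and this is repeated 10,000 times for each n. The section concludes that "we can identify the smallest sample size that achieves 90% power". It mentions no dropout, no censoring and no later inflation of n.

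Other sections of the SAP bear on this:

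- Section 7 separates evaluable from recruited children. It finds 79 evaluable per group and then adds: "We will aim to recruit 176 subjects total to allow for up to a 10% dropout rate".
- Section 8.5.6: "The final analysis of the primary outcome uses the remaining alpha not used (0.05 minus the amount used in the interim, 0.0045"). Section 10.1 repeats the subtraction.
- Section 8.4 censors children on methotrexate whose MISS scores are missing. Sections 9.3 and 10.1 expect some children to have no documented 12-month endpoint and use Kaplan-Meier estimates for that reason. Section 15 applies the same method, with a Wald interval on the log scale, to the final analysis.
- Section 15 reports 27 children with a determined outcome at the interim and 17 more still in follow-up. It gives no results by arm.

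**The concern.** The re-estimation answers a question about enrolment with a calculation about evaluable children. Section 7 makes that distinction and inflates for it; section 8.5.7 does not. By the time of the re-estimation the SAP already accepted that some children would lack an endpoint and had changed its estimator for that reason, yet each simulated child has a known outcome. The interval is also slightly narrower than the one the final alpha allows.

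Section 8.5.8 has the sponsor weigh the newly calculated sample size against funding and recruitment, following the committee's recommendation. If that n is labelled as giving 90% power and gives less, the decision rests on a mislabelled figure.

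**Working it through.** **Inputs.** Success 75% v 50%, target 90% power, 95% interval above 1.2 (section 8.5.7); dropout up to 10% and 79 evaluable per group (section 7); final alpha 0.05 − 0.0045 = 0.0455, z = 2.000 (section 8.5.6); 1:1 allocation (section 6.3); 27 determined at interim (section 15).

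**1. The plan's own figure.** With log-RR and a pooled null variance, n = (1.960·√1.2 + 1.282·√1.333)² / ln(1.5)² = 80.0 per group, within 2 of the stated 79. Inflation: 158 / 0.9 = 175.6, so 176, exactly as stated. The 79 is therefore an evaluable number and 176 an enrolment number. The SAP prints no n for the re-estimation.

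**2. Section 8.5.7 as written, by formula, ignoring interim data.** The variance term is v = 0.25/0.75 + 0.5/0.5 = 1.333, and the distance to the target is ln(1.5/1.2) = 0.2231.

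n = (1.960 + 1.282)² × 1.333 / 0.2231² = 281.4, so 282 per arm.

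Power = Φ(0.2231 / √(1.333/n) − z):

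| Evaluable per arm | z | Power |
|---|---|---|
| 282 | 1.960 | 90.1% |
| 282 | 2.000 | 89.3% |
| 253.8 (10% lost) | 1.960 | 86.8% |
| 253.8 (10% lost) | 2.000 | 86.0% |

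Restoring 90% at alpha 0.0455 takes 288.4, so 289 evaluable per arm, or 289 / 0.9 = 321.1, so 322 enrolled per arm if dropouts contribute nothing.

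**3. Binomial simulation with interim data added** (40,000 replicates per cell). The splits of the 27 are assumptions. The 17 children in follow-up are left out.

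| Assumed interim result | New n per arm | As written | Alpha 0.0455 | 10% lost | Both |
|---|---|---|---|---|---|
| None used | 268 | 90.4% | 89.5% | 86.7% | 85.9% |
| 10/14 v 7/13 | 262 | 90.2% | 89.0% | 86.9% | 85.8% |
| 8/14 v 8/13 | 304 | 90.1% | 89.5% | 86.2% | 85.4% |
| 7/14 v 9/13 | 328 | 89.8% | 89.0% | 85.5% | 84.6% |
| 12/14 v 5/13 | 202 | 89.8% | 89.4% | 88.0% | 86.8% |

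Cells carry a Monte Carlo standard error of about 0.15 to 0.2 points and were drawn separately. Repeating with 400,000 replicates and the same draws for both intervals puts the alpha cost at 0.7 to 0.8 points at the 1.2 target. With the smaller n of a target of 1 it is uneven because counts are discrete; the largest seen was about 1.4 points.

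**4. Kaplan-Meier simulation**, which is closer to the planned final analysis: Greenwood variance, log-scale Wald interval, 10,000 replicates, no interim data. It uses n = 268, the figure simulation returns, because section 8.5.7 prescribes simulation. Without dropout and with a 95% interval, power is 90.1%. With 10% dropout and alpha 0.0455:

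- all dropouts leave at time zero: 86.1%;
- dropout uniform over 52 weeks, constant failure hazard: 87.5%;
- dropout uniform over 52 weeks, failures concentrated early: 88.4%.

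The standard error is about 0.3 points. A 30,000-replicate repeat gave 86.2%, 87.8% and 88.1%.

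**The case against.** Four points can be made for the plan.

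- **Dropout is absent by silence only.** Section 7 works in two steps, and the n of section 8.5.7 might be inflated afterwards too. In that case only the alpha mismatch remains (89.3% by formula). This is possible, but section 8.5.7 runs from question to answer, speaks of enrolment, treats the result as the power for n new patients, and describes no such step.
- **The 95% may be a loose label.** Each replicate runs the final analysis, and section 10.1 itself names a 95% interval before reducing alpha. That is fair, and the cost is small either way. It does not supply the missing dropout.
- **A reader might infer a flat 86%.** The documents do not support that. Section 7 says up to 10%, and the Kaplan-Meier analysis keeps each child's follow-up until censoring. About 86% needs the full 10% lost with no information contributed.
- **A reader might infer that the primary test is underpowered.** That does not follow. Section 10.1 rejects when the interval lies above 1, and at an n chosen for 1.2 the power of that test exceeds 99.9% even with dropout and the reduced alpha. The shortfall concerns the 1.2 target. If the target became 1 and n were re-solved, a similar shortfall would return.

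It is also fair to say that a few points of power may not change a decision dominated by slow recruitment. That bears on urgency, not on whether the stated 90% is right.

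**Conclusion.** The point holds in a limited form. Followed as written, section 8.5.7 gives an enrolment number that falls short of its own 90%: about 86% to 88.5% when 10% drop out, before interim data are added. The low end assumes dropouts contribute nothing; 87.5% to 88.4% assumes dropout spread evenly over 52 weeks. With assumed splits of the 27 determined children, the contribute-nothing case runs from 84.6% to 86.8%. By formula, dropout alone costs about 3.3 points (90.1% to 86.8%).

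The figures assume no later inflation of n, dropout at the section 7 ceiling and unrelated to outcome, and true rates of 75% and 50%. No printed sample size is shown to be wrong, since the SAP gives no re-estimated n. The choice between 1.2 (section 8.5.7) and 1 (section 10.1) moves n far more and is a separate matter.

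**What to change.** First reconcile the 1.2 target in section 8.5.7 with the rejection rule of 1 in section 10.1. Then re-run the simulation as follows:

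- draw failure times and censoring, with dropout at the section 7 rate and its assumed timing stated;
- analyse each replicate with the Kaplan-Meier log-RR interval at alpha 0.0455;
- carry the 17 partly followed children forward with the follow-up they have, not as resolved outcomes;
- say whether n means enrolled or evaluable children.

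Report either the number to enrol for 90% power or the power that the chosen number delivers. If n was in fact inflated for dropout, one sentence saying so removes most of the problem.

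The cost is a few lines of simulation code and one restated figure. By formula at the 1.2 target, keeping 90% would take up to 322 rather than 282 enrolled per arm, and fewer if dropouts contribute follow-up. Keeping n fixed means quoting a power a few points lower.

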8.5.8 Practical Measures to Minimize Bias

The interim analysis is conducted by a PhD student in the Department of Statistics and Actuarial Science at Simon Fraser University, working under the direct supervision of the study statistician. Neither the statistician nor the student has a financial stake in the outcome of the trial. They receive only the data necessary to conduct the analysis and confirm its accuracy.

The results of the interim analysis are presented to the DSC by the study statistician and the DSC is charged with making a recommendation to the PI as to the advisability of continuing the trial.

OPT-JIA does not have a pharmaceutical sponsor and all medications tested in the trial are medications currently marketed in Canada and available as generic medications. The study PI, [name], serves as the trial sponsor in Health Canada submissions.

As per the OPT-JIA DSC Charter, [name] will consider the recommendation of the DSC. If the recommendation is to continue the trial to attain the newly calculated sample size, [name] will consider the feasibility of this approach given available study funding and the observed recruitment rate. No information will be made public until a final determination is made.

Because the intervention requires all parties in the trial to act differently from the control, there is no blinding in the trial, and hence no need for additional measures during the statistical analysis to preserve blinding.

8.5.9 Documentation of Interim Analyses

All interim analysis data files, preliminary statistical output and final interim analysis report for the DSC will be preserved in the OPT-JIA Trial folders at the institutional computer servers controlled by the BC Children's Hospital in Vancouver, under the custody of [name]. Copies of all email communications pertaining the interim analysis between the study biostatisticians, study PI and the chair of the DSC will also be preserved in these folders.

9 Summary of Study Data

All variables will be summarized separately for subjects assigned to the intervention and to the control group and shown in side-by-side columns in tables in that order. Descriptive categorical variables at baseline will be summarized as frequencies and percentages. Descriptive continuous variables at baseline will be summarized as medians and 25th and 75th centiles. Efficacy categorical variables will be summarized as frequency and percentages. Efficacy continuous variables (MISS scores and quality of life scores) will be summarized as means and standard deviations.

Between-groups comparisons of baseline characteristics will be made using Fisher exact tests for categorical variables and the Wilcoxon rank sum test for continuous variables, and the corresponding p value reported. All tests will be double sided and p values <0.05 will be considered statistically significant.

9.1 Subject Disposition

Subject disposition will be reported as per the CONSORT statement [19] using the skeleton chart reproduced in Figure 2.

[figure not shown]

Figure 2: CONSORT flow diagram of trial participants.

9.2 Derived variables

Methotrexate intolerance is one of the two criteria used to determine patient failure during the trial. Intolerance is defined as ≥ 6 points in the English or French versions of the validated Methotrexate Intolerance Severity Score, MISS [1,2]. The MISS questionnaire is the sum of 12 items, each scored from 0 to 3, for a total possible score of 36 points. A derived variable named INTOLERANCE takes the value of 1 if a MISS score of 6 or more was ever recorded for a patient, or zero otherwise.

We determined weeks on trial as the number of weeks elapsed between the visit date and the date of enrolment in the trial.

9.3 Protocol Deviations

1. Patient exclusions: The primary analysis is an intention to treat analysis. As such, a randomized patient can only be excluded from the primary analysis in exceptional circumstances, such as the diagnosis of JIA proves to be wrong, or the patient was included in violation of the inclusion and exclusion criteria for the trial. For further clarity, a patient randomized to intervention cannot be excluded because they did not take ondansetron or because they withdrew from the trial. A patient randomized to control cannot be excluded because they took ondansetron or because they withdrew from the trial. To preserve the

integrity of an intention to treat analysis it thus follows that all randomized patients should have a value for the primary endpoint. Due to OPT-JIA study design with no fixed date visits and missing data, it was clear at the time of the interim analysis that there would be patients with no documented endpoint at 12 months. Instead of imputing the endpoint as failure for subjects with no documented endpoint at 12 months or having their last recorded information carried forward, it was decided to use Kaplan Meier estimates of the probability of success at 12 months as these account best for censored patients and missing information.

The secondary per protocol analysis will include all patients that received the assigned intervention for at least 3 months or who experienced intolerance within the first three months. For the intervention group this means the patient received methotrexate and prophylactic ondansetron for at least 3 months. For the control group this means the patient received methotrexate for at least 3 months. Patients that withdraw or are lost to follow-up before 3 months are not included in the per-protocol analysis, unless they already experienced intolerance or toxicity. Patients who withdraw or are lost to follow-up after 3 months will be considered censored and have their data analyzed using Kaplan Meier survival methods.

2. Analysis changes: Because the interim analysis would be based on a much smaller fraction of the intended sample size, the study PI and statistician proposed, and the DMC agreed, to base the interim analysis on the confidence interval for relative risk computed using the ratio of two estimates of the probability of successful trial completion from independently estimated Kaplan Meier curves. These estimates would better account for the partial information available from patients with incomplete information due to insufficient time in the study to complete the 52-week observation period. After it became clear during the interim analysis that some patients will not have a documented endpoint, it was decided that Kaplan Meier estimates will also be used in the final analysis.

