8.2 Analysis Populations

(ICH E3; 9.7.1, 11.4.2.5. ICH E9; 5.2)

The primary analysis will be conducted on the intention-to-treat population, including all randomized subjects. A secondary per-protocol analysis will be conducted on those subjects who received the assigned intervention for at least 3 months (ondansetron and methotrexate in the intervention group, methotrexate in the control group). Because it was clear at the time of interim analysis that some patients stopped methotrexate before 3 months due to intolerance, the per protocol analysis was modified to also include patients who stopped the medication before 3 months due to intolerance or toxicity.

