10.2 Secondary Efficacy Analyses

There will be one secondary per-protocol efficacy analysis comparing all intervention and control subjects who received the assigned intervention for at least 3 months. The per-protocol analysis will be identical to the intention to treat analysis, except for the number of subjects included. For further clarity, it will consist of analyses of the same primary endpoint and five secondary endpoints, but only subjects that received the assigned intervention for 3 months will be included in comparisons. Because some patients may stop methotrexate due to intolerance before 3 months it was decided to conduct a modified per protocol analysis. The modified per-protocol analysis will include all patients receiving study medications for at least 3 months and all patients stopping medications before 3 months due to intolerance or toxicity. Physicians and parents are asked to report in separate case report forms if the patient is receiving ondansetron. If information is missing from one source, the other source will be considered true. If information is missing from both sources, the site investigator will be asked to verify ondansetron status against their clinical records.

11 Safety Analyses

OPT-JIA will assess the safety and tolerability of premedication with ondansetron, compared to as needed use. The safety endpoints are the frequency and cumulative incidence of adverse events and any serious unexpected suspected adverse drug reactions (SUSARs). Safety parameters in the OPT-JIA trial will be assessed using the standard set of questions about adverse events that are part of the CAPRI JIA Registry. These questions will be asked from the attending physician every time the study participant attends the pediatric rheumatology clinic for a medical visit. The form lists the following adverse events: abdominal pain, nausea/vomiting, rash (not JIA rash), injection reaction, infusion reaction, gastrointestinal bleed, abnormal blood counts, abnormal liver function tests, anaphylaxis, infection with hospitalization, tuberculosis, opportunistic infection, demyelinating disease, inflammatory bowel disease, malignancy, gastrointestinal perforation, eye surgery, joint surgery, and macrophage activation. Any non-listed events are reported as "Other / Not listed" by entering a description of the adverse event.

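### SAP 9.3 admits intervention children who did not take ondansetron to the per-protocol set only if they become intolerant within 3 months, a dependence on outcome that controls do not face

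*SAP*

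**What the plan says.** SAP 9.3 (Protocol Deviations) defines the per-protocol set as "all patients that received the assigned intervention for at least 3 months or who experienced intolerance within the first three months". It then explains the 3-month condition by arm:

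- Intervention: "For the intervention group this means the patient received methotrexate and prophylactic ondansetron for at least 3 months".
- Control: "For the control group this means the patient received methotrexate for at least 3 months".

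Children who withdraw or are lost before 3 months "are not included in the per-protocol analysis, unless they already experienced intolerance or toxicity". This rule is the same in both arms.

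Three other places word the early-failure route differently. SAP 8.2 says the set was "modified to also include patients who stopped the medication before 3 months due to intolerance or toxicity". SAP 10.2 adds "all patients stopping medications before 3 months due to intolerance or toxicity", and the introduction to SAP 10 also refers to stopping medications. The stated reason for the change is in 10.2: "Because some patients may stop methotrexate due to intolerance before 3 months it was decided to conduct a modified per protocol analysis".

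Under SAP 10.1 any MISS score of 6 or more within 52 weeks is a failure of the primary endpoint. Stopping ondansetron or methotrexate for toxicity or lack of efficacy is also a failure.

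**The concern.** There are two routes into the set, and only the first asks whether the assigned treatment was taken. The ondansetron part of that condition applies in one arm only. Consider a child on methotrexate for 3 months or more who does not take prophylactic ondansetron:

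| Course | Intervention arm | Control arm |
|---|---|---|
| Intolerant before 3 months | included, as a failure | included, as a failure |
| Fails after 3 months | excluded | included, as a failure |
| Does well for the year | excluded | included, as a success |

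Among intervention non-takers only early failures survive the selection. A control child on methotrexate stays in regardless of ondansetron use.

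A reader of an open-label, pragmatic trial will look to the per-protocol result for the effect in children who followed the assigned strategy. This set does not isolate those children. The mismatch in triggers is a separate problem: two programmers could build different sets from the same SAP.

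**Working it through.** **The plan's own figures.** The SAP gives no figure for the per-protocol set. Section 7 supplies expected success of 50% in control and 75% in intervention (RR 1.50), with 79 evaluable children per group. A log-RR formula with pooled variance for alpha and alternative variance for power gives

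n = [1.96·√(2·0.375/0.625) + 1.2816·√(0.5/0.5 + 0.25/0.75)]² / (ln 1.5)² = 80.0,

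close to 79; and 158/0.9 = 175.6, rounded up to 176. The 50% and 75% are therefore used below.

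**Assumed inputs (not in the SAP).**

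- q: share of the intervention arm on methotrexate but not taking ondansetron as assigned, 10-30%.
- e: share of those non-takers intolerant before 3 months, 15-35%. If non-takers succeed at 50%, e = 25% puts half of their one-year failures in the first 3 months.

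**Formula.** With p_T the takers' success rate, the non-takers kept are all failures, so

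per-protocol success = (1−q)·p_T / [(1−q) + q·e], and RR = that / 0.50.

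The denominator exceeds (1−q) whenever q and e are above zero, so the result is always below p_T.

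**Worked case, no effect.** Take 80 per arm, q = 20%, e = 25%. There are 64 takers with 32 successes. Of 16 non-takers, 4 early failures are kept and 12 dropped (8 eventual successes and 4 later failures). Success is 32/68 = 47.1%, RR 0.94.

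**Range.** Non-takers are given 50% success; ITT success under the planned effect is (1−q)·0.75 + q·0.50.

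| q | e | RR, no effect | RR, planned effect | ITT RR, planned effect |
|---|---|---|---|---|
| 10% | 15% | 0.984 | 1.475 | 1.45 |
| 10% | 35% | 0.963 | 1.444 | 1.45 |
| 20% | 15% | 0.964 | 1.446 | 1.40 |
| 20% | 25% | 0.941 | 1.412 | 1.40 |
| 20% | 35% | 0.920 | 1.379 | 1.40 |
| 30% | 15% | 0.940 | 1.409 | 1.35 |
| 30% | 35% | 0.870 | 1.304 | 1.35 |

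**If non-takers have a worse prognosis.** Under no effect, hold the whole intervention arm at 50% and let non-takers succeed at p_N. Then (1−q)·p_T = 0.5 − q·p_N, and RR = 1 exactly when p_N = 0.5·(1−e). That is 42.5%, 37.5% and 32.5% for e = 15%, 25% and 35%. Below this the sign reverses: q = 20%, e = 40%, p_N = 25% gives RR 1.02.

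**The two triggers.** An intervention non-taker with a MISS of 6 or more who continues methotrexate is in under 9.3 and out under 8.2, 10 and 10.2. A non-taker who stops methotrexate for intolerance can be in under all of them, since none requires that ondansetron was being taken. The narrower trigger therefore lowers e without necessarily bringing it to zero. At q = 20%, e = 10%, the no-effect RR is 0.80/0.82 = 0.98.

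**The case against.** The strongest reply is that the problem rests largely on one sentence in 9.3. The wording of 10.2 pairs stopping medications with receiving study medications, which suggests they were being taken; aligning 9.3 with it would remove much of the scenario. Much, but not all: in 8.2 the medication in question is, in context, methotrexate, so an ondansetron non-taker who stops it for intolerance still enters.

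Second, q and e are not in the SAP, and small values make the distortion small. That stands, and is why a range is shown.

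Third, a reader might infer that the set is biased against premedication without qualification. The documents do not support that. The shortfall against takers is certain for any positive q and e. A shortfall against the null needs non-takers to have a broadly similar prognosis, which the SAP does not address.

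Fourth, a reader might infer that the per-protocol result will part from intention to treat. It need not: at q = 20% and e = 25% the planned-effect figures are 1.41 and 1.40.

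Fifth, it is tempting to say that the rule removes only children who did well. It also removes non-takers who fail after 3 months. And children who stop ondansetron for toxicity or lack of efficacy are failures under 10.1, so they are not dropped successes.

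The purpose of the modification, not losing genuine early failures, is sound.

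**Conclusion.** The point holds as a defect in the stated rule. Entry to the per-protocol set depends on outcome through an ondansetron condition found in the intervention arm only, and no other section cures it.

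Under the assumed 10-30% non-taking and 15-35% early failure, the RR is 1.48 to 1.30 where takers have 1.50. With no effect it is 0.98 to 0.87, conditional on similar prognosis. The conflict between experiencing intolerance and stopping medication needs no assumption: the sections define different sets.

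A reader might carry this over to the trial's main conclusion. That is not supported: the primary analysis is intention to treat, and no stopping or success rule rests on the per-protocol set. It should be corrected before the final analysis, but it does not threaten the primary result.

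**What to change.** In SAP 8.2, 9.3, 10 and 10.2, state one trigger for early failure and one exposure condition that applies whatever the outcome:

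- An intervention child, failing or not, enters only if methotrexate and prophylactic ondansetron were started as assigned. A control child enters only if methotrexate was started.
- A child who leaves the assigned strategy before 3 months while well, for a reason that 10.1 does not count as failure, is censored at that point in the planned Kaplan-Meier analysis rather than excluded.
- Controls are not excluded for ondansetron use unless use before any reported nausea or vomiting can be identified from the recorded data. As-needed use is part of the control strategy (6.1, 6.3) and follows the same dosing and schedule once prescribed, so a looser rule could remove controls who had symptoms and create a new selection on outcome.

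Requiring adherence only up to the time of failure, but a full 3 months from children who stay well, would not be enough: entry would still depend on outcome. In the simple model above, one exposure condition for all returns RR 1.00 under no effect and 1.50 under the planned effect when prognosis is similar.

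The cost is SAP wording. Physicians and parents already report ondansetron use, and 10.2 has a rule for missing reports. The downside is a somewhat different per-protocol set and reliance on the new censoring being non-informative, which the SAP should acknowledge.
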